## Summary of the Clinical Trial Protocol and Statistical Plan

Name of Sponsor/Company:	AiCuris Anti-infective Cures GmbH	
Title of the trial: A randomized, double-blind, multi-center, three arm (pritelivir, placebo and Zovirax ® ) parallel group, comparative trial to assess the efficacy and safety of pritelivir 5% w/w ointment for the treatment of recurrent herpes labialis in adults – LipP 1		
Trial center(s): 10 to 14 investigational sites in the US		
Planned study period (years): First Subject First Visit: 4 th quarter 2016 Last Subject Last Visit: 3 rd quarter 2017	Phase of development: 2	
Objectives: To assess the efficacy, tolerability and safety of pritelivir 5% w/w ointment applied 5 times daily for 4 days for the treatment of recurrent herpes labialis (rHL) in adults		
Trial design: This is a randomized, double-blind, multi-center, three arm parallel group, comparative trial to assess the safety and efficacy, ie, proportion of subjects with non-ulcerative lesions, in adult subjects with rHL treated with pritelivir 5% w/w ointment. The statistical superiority will be tested against placebo and a descriptive comparison with Zovirax ® Cream will be made. The start of treatment with trial medication will be initiated by the subject within one hour of noticing the first sign or symptom (eg, prodrome) of a recurrence of herpes labialis (HL). Trial medication will be applied to the affected area 5 times daily for 4 days.		
Number of subjects (planned): approx. 360 subjects should be enrolled resulting in at least 71 subjects dosed in each treatment arm.		

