**Criteria for evaluation:**

**Efficacy:**

[figure not shown]
Primary endpoint:

- The percentage of subjects with non-ulcerative lesions in each treatment group.

Secondary endpoints:

- Duration of lesion episode (DOE), defined as time from treatment initiation to the healing of the primary lesion (loss of crust) for subjects who experienced a vesicular lesion. For subjects whose primary lesions were not vesicular in nature, DOE is the time from the treatment initiation to the return to normal skin or to the cessation of symptoms, whichever occurs last;
- Pain rate, defined as number of days with pain at lesion site relative to the total number of days with analyzable pain through daily subject self-assessment;

- Subject-assessed duration of lesion pain, defined as the time from first dose of trial medication until pain is no longer reported by the subject (date and time);
- Subject-assessed severity of lesion pain defined as the average daily NUMERICAL RATING SCALE (NRS) pain score using a single-dimensional scale assessing pain intensity at lesion site, 11 intensities [no pain (0) to worst pain imaginable (10)];

- Maximum lesion area (length x width) for ulcerative lesions during the vesicular, ulcerative and hard crust stages;
- Cumulative lesion area (sum of daily maximum lesion areas);
- Duration of lesion tenderness (unpleasantness upon touching the affected area).

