**Methodology:**

**Efficacy measurements:**

After self-initiation of treatment with trial medication subjects will be assessed daily for the following parameters by the Investigator until healing:

1. Lesion stage:
  - prodrome (symptoms including itching, pain, tingling, but no physical evidence of disease by inspection or by palpation in the application area),
  - erythema
  - papule (any elevation of skin without fluid in the application area)/edema,
  - vesicle (blister, fluid filled or collapsed, in the application area),
  - ulcer/soft crust,
  - hard crust,
  - residual abnormalities (residual erythema/scaling),
  - normal appearing skin.

2. Maximum lesion area (length x width) in mm^2

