**Subject diary documentation:**

Subjects will document the following in their diary:

1. Time of each application of trial treatment,
2. Pain intensity, changes in pain intensity, and cessation of pain at each application of trial treatment (at the first and last daily application as a minimum),
3. Pain intensity, changes in pain intensity, and cessation of pain in the morning and evening on days after stop of application of trial treatment until pain disappeared,
4. Lesion stage at each application of trial treatment,
5. Lesion stage in the morning and evening on days after stop of application of trial treatment until lesion healing,
6. Lesion tenderness at each application of trial treatment, and,
7. Lesion tenderness in the morning and evening on days after stop of application of trial treatment until lesion tenderness disappeared.

Subject diaries will be reviewed by the investigational site staff at each visit.

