**Statistical methods:**

**Sample size calculation:**

The primary endpoint will be the percentage of subjects with non-ulcerative lesions in each treatment group.

The percentage of subjects with non-ulcerative lesions if left untreated with HL is estimated as 26%. The percentage of subjects with non-ulcerative lesions is assumed to be 50% when applying pritelivir 5% w/w ointment as compared to placebo. The following table shows the total number of subjects with recurrences needed to show superiority of pritelivir compared with placebo with 80% power and assuming a type I error rate of 5%.

Proportion of subjects with non-ulcerative lesions:		Total number of evaluable recurrences needed 1:1:1 randomization			Total evaluable recurrences needed	Total number of subjects needed (including 40% who do not develop a recurrence)
Placebo	Pritelivir	Pritelivir	Placebo	Zovirax®		
26%	50%	71	71	71	213	360

It is assumed that 71 recurrences in each arm are sufficient to allow for a descriptive comparison of pritelivir with Zovirax®.

In order to obtain 213 evaluable HL recurrences, 360 subjects need to be randomized in a 1:1:1 randomization scheme to cover the rate of approx. 40% of subjects which do not develop a recurrence or drop out.

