**Primary efficacy analysis:**

The primary efficacy analysis will be performed in the ITT (Intend to Treat Set) and the PPS (Per-Protocol Set).

ITT includes the results from all randomized subjects who applied the trial medication at least once and had at least one lesion status assessment done/reported after start of treatment.

PPS is a subset of the ITT excluding subjects with major protocol violations.

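### Does the one-assessment ITT rule let an episode whose staging stops early count as a primary-endpoint success?

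*Combined protocol and SAP*

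**What the plan says.** The primary endpoint, under Criteria for evaluation, Efficacy, is "The percentage of subjects with non-ulcerative lesions in each treatment group". No list of ulcerative stages, time window or completeness condition goes with it.

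Under Primary efficacy analysis, the ITT requires randomization, one application, and that the subject "had at least one lesion status assessment done/reported after start of treatment". The same section runs the primary analysis in the PPS too, which removes major protocol violations without listing them.

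Two sources of staging are planned to the end of the episode. Under Efficacy measurements, "subjects will be assessed daily for the following parameters by the Investigator until healing". Under Subject diary documentation, subjects record "Lesion stage in the morning and evening on days after stop of application of trial treatment until lesion healing".

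On numbers, the Summary says "approx. 360 subjects should be enrolled resulting in at least 71 subjects dosed in each treatment arm", while Sample size calculation says "In order to obtain 213 evaluable HL recurrences, 360 subjects need to be randomized". The latter sentence goes on to explain the excess over 213 by the roughly 40% who have no recurrence or drop out. The table header beside it attributes the 40% to non-recurrence alone. The term evaluable is not defined.

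**The concern.** Treatment starts within an hour of the first sign or symptom, so the first lesion assessment will often come before an ulcer could have formed. A subject staged once at papule and then lost meets the ITT rule, and nothing on record contradicts a non-ulcerative outcome. If the database default is no ulcer recorded means success, incomplete follow-up is rewarded. Pritelivir against placebo on this endpoint is the only comparison tested for superiority, so a scoring choice made after unblinding could follow the result. If truncation also differed between arms, the error in the estimated difference could go either way.

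**Working it through.** **Inputs.** From Sample size calculation: 26% non-ulcerative on placebo, 50% on pritelivir, 71 evaluable recurrences per arm, 80% power, 5% type I error (taken as two-sided, because that reproduces the stated size), 360 randomized, about 40% lost. Assumed, because the document gives no figure: a share d of episodes whose staging stops before any ulcer is recorded, independent of true outcome. The primary test is not named; Fisher's exact test is used because it fits the stated power.

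**Plan's own figures.**
- The two-proportion formula with continuity correction gives 71.1 per arm (63.0 without it), against 71 stated.
- Exact Fisher power at 71 per arm is 79.8%, against 80% stated.
- 213 / (1 − 0.40) = 355, against 360 stated. Conversely, 360 × 0.60 = 216 expected, which is 3 more than 213.

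The size is sound.

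**Equal truncation in both arms.** The observed rate is p(1 − d) + d if truncated episodes are scored success and p(1 − d) if scored failure. If they are excluded, p is unchanged and n falls: 5% of 71 is about 4, leaving 67; 10% is about 7, leaving 64.

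At d = 5%:
- success: 0.26 × 0.95 + 0.05 = 29.7% vs 0.50 × 0.95 + 0.05 = 52.5%
- failure: 24.7% vs 47.5%

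At d = 10%:
- success: 33.4% vs 55.0%
- failure: 23.4% vs 45.0%

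| d | Success | Failure | Excluded |
|---|---|---|---|
| 0% | 79.8% | 79.8% | 79.8% |
| 5% | 74.4% | 76.2% | 77.6% |
| 10% | 69.0% | 72.5% | 76.4% |

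Entries are exact Fisher power. The spread across scoring rules is 77.6 − 74.4 = 3.2 points at 5% and 76.4 − 69.0 = 7.4 points at 10%. With no true effect (26% in both arms), the chance of a significant result favouring pritelivir is 1.5% to 1.6% in every cell. Success scoring with equal truncation dilutes the effect; it does not manufacture one.

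**Unequal truncation.** With shares dT (pritelivir) and dP (placebo), the error in the difference lies between −dP and +dT under success scoring, and between −dT and +dP under failure scoring. With no true effect, false pritelivir wins are:
- dT = 10%, dP = 2%: 8.5% scored success, 0.7% scored failure.
- dT = 2%, dP = 10%: 0.2% scored success, 3.1% scored failure.

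Failure scoring therefore has its own exposure, above the nominal 2.5% per side in the second case. With the true 24-point effect and 10% vs 2% truncation, it gives 0.50 × 0.90 − 0.26 × 0.98 = 19.5 points. Reversed, it gives 0.50 × 0.98 − 0.26 × 0.90 = 25.6 points.

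**Fragility near the planned result.** 36/71 vs 18/71 gives Fisher p = 0.003. Turning 5 pritelivir successes into failures gives p = 0.034; 6 (8% of the arm) gives p = 0.0504. Recoding 9 in each arm (27/71 vs 9/71) gives p = 0.0009, a stronger result. Only one-sided recoding threatens the conclusion.

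**Does the text choose success?** The endpoint counts subjects with non-ulcerative lesions, not subjects without an ulcer on record. The lesion-stage list describes prodrome as having no physical evidence of disease, so an episode last seen at prodrome has no recorded lesion of either kind. The sample-size sentence takes out dropouts before reaching 213 evaluable recurrences, which leans towards exclusion. On that reading, 216 is already net of dropout, and the margin of 3 is not a further constraint.

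**The case for a change.** The strongest case for acting is that the visit and diary schedules are plans for measurement, not conditions of the endpoint or of ITT entry. The one-assessment threshold itself admits subjects who did not complete them. Evaluable is undefined, and the Summary calls the same 71 per arm dosed. The PPS is only a partial check, because the major violations are not listed, and it does nothing for the ITT result. Nor is brevity a full answer: the same summary spells out how the episode ends for a secondary endpoint, separately for vesicular and non-vesicular lesions. Six one-sided reclassifications could decide the test, and a rule would cost a few sentences.

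All of that stands as a description of what is missing. It does not show that the plan's rule is wrong, since there is no rule to be wrong. Nor does it identify a better one. Scoring incomplete episodes as failures has less power than exclusion at both assumed rates, can exceed the nominal error rate if truncation falls mainly on placebo, and can understate a true effect. Sensitivity tables and a list of stages counted as ulcerative would add to the write-up without correcting an error.

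**Conclusion.** The concern does not call for a change. The document is headed as a summary and leaves open how an episode with incomplete staging is scored; it does not make such an episode a success. Both staging sources would have to stop before healing for the question to arise. The remaining wording (evaluable, dropouts within the 40%) points towards exclusion, and the PPS gives a second, partial look. Analysts would ordinarily settle the convention in blinded data review before the code is broken.

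Under assumed equal truncation of 5% to 10%, the choice is worth about 3 to 7 points of power, with false wins near 1.6%. Larger effects need truncation that differs materially between arms, and nothing in the document suggests it. These figures rest on 71 per arm, rates of 26% and 50%, a two-sided Fisher's exact test, and truncation independent of true outcome. If the trial data showed clearly unequal truncation by arm, the scoring rule would matter to the interpretation of the result.

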**Secondary efficacy analyses**

The secondary efficacy analyses will be performed in the ITT and the PPS.

**Safety**

All safety and tolerability parameters will be listed. All safety analyses will be performed in the Safety Set (= all randomized subjects who applied at least one dose of trial medication).
